Each sachet will be dispensed to a member of the study team just prior to the participant's study visit and recorded by the Pharmacy staff including the date, participants ID number and dosage for accountability. Participants will receive two single administration doses of the *Centella asiatica* product equivalent to 2g and 4g of *Centella asiatica* water extract. The order in which they receive these doses will be random to prevent a tolerance effect. The doses selected are based on allometric scaling¹⁰⁴ from previous murine studies, which showed that 1.4 g/day of *Centella asiatica* water extract for a 70 kg human was equivalent to the 200 mg/kg/day estimated intake in mice. Participants will consume CAP in the presence of a member of the research team following baseline measurements, in order to ensure adherence to the study protocol. Following study completion, the remaining intervention and placebo sachets will be provided to [name] for destruction.

H.2. Administration

The study intervention will be administered in an outpatient setting. The research pharmacy will dispense one dose of CAP to a member of the study team, who will reconstitute the CAP powder in 8-12 ounces of warm water and provide it to the participant for oral consumption. One dose will be administered at each study visit in a random order.

H.3. Modification to study intervention

There will be no modifications to the study intervention during the study unless there are adverse events are noted and recommendations are made by the study's Independent Monitoring Committee (IMC).

Figure 4: Redacted

H.4. Criteria for intervention discontinuation and stopping guidelines

Participants will be advised during the informed consent process that they have the right to permanently discontinue the *Centella asiatica* product and/or withdraw from the study at any time without negative repercussions. Participants will also be counseled during the consent process that they may be withdrawn from the study at the discretion of the Principal Investigator or designees. A participant may discontinue and/or withdraw and/or be withdrawn from the study for the following reasons:

Administrative:

- 1) Withdrawal of participant consent
- 2) Request of site investigator or designees
- 3) Request of primary care physician
- 4) Non-compliance
- 5) Protocol deviation
- 6) Premature termination of the study

Study Title: A pharmacokinetic study of *Centella asiatica* in the elderly

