Principal Investigator: [name]

IRB#: 17697

Date: Feb 28 2024

Protocol v4.0

Adverse event (AE)/experience:

- 1) Worsening of pre-existing disease
- 2) Intercurrent illness
- 3) Death
- 4) Major/clinically significant alteration in laboratory values or biometric assessments after beginning product
- 5) Other AE
- 6) Other reasons concerning the participant's health or well-being

The study will be terminated if two participants terminate due to intervention-related adverse events. Severe adverse events will be reviewed immediately by the Principal Investigator, clinical investigators and the Independent Monitoring Committee (IMC) to determine if severity and relatedness warrant termination of the study (Section N).

I. SCREENING AND STUDY ACTIVITIES

I.1. Phone screening

Potential participants will be screened over the phone by a member of the study team, primarily the study coordinator, prior to coming in for the in-person screening visit. A standardized telephone script will be used and has been submitted for IRB approval. The telephone screening will take approximately 10-15 minutes. Potential participants that meet eligibility criteria (Section F.2.2) over the phone will be scheduled for a screening visit.

I.2. Consent process

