To ensure full comprehension of all aspects of their participation in the study, all potential participants will be mailed a copy of the IRB approved consent and HIPAA form prior to their in-person screening visit. They will be instructed to review the form ahead of time but not to sign it until the visit. All in-person screening visits and consenting will occur in a CTRC outpatient room. At the in-person screening visit, a member of the study team will review the consent/HIPAA form and then will ask the participant to describe key points in the form (e.g. purpose of study, dietary requirements, length of study) before signing. After the participant signs the consent, the participant will continue with screening assessments and baseline measurements. A physical copy of their consent form will be provided to each participant and kept in the affiliated study folders to be made available as necessary to an Independent Monitoring Committee or the OHSU IRB. To ensure ongoing consent, participants will be called three days prior to their second study visit to ask if they wish to continue their participation in the study. At this time, participants will also be reminded of their upcoming study visit, to stop necessary supplements, and begin the necessary dietary changes (Section I.4.). Appropriate language will be included in the consent form to avoid coercion. We will underscore that they can decline to participate at any point in the study, even if they have signed the consent form, and it will not impact their participation in future research trials.

I.3. Screening visit

The participant's health status will be evaluated by a study clinician using a biometric assessment (blood pressure, height, weight and body mass index), vital signs (pulse rate and temperature), a screening exam, a mood assessment (Geriatric Depression Scale-15) and cognitive assessments (Clinical Dementia Rating and Mini Mental State Examination). A non-fasting plasma and urinary laboratory evaluation (complete blood count, comprehensive metabolic panel and urinalysis) will be performed and submitted to the OHSU clinical core laboratory to identify asymptomatic illnesses that could impact study results (Table 2). A

Study Title: A pharmacokinetic study of *Centella asiatica* in the elderly

Principal Investigator: [name]

IRB#: 17697

Date: Feb 28 2024

Protocol v4.0

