member of the study staff with venipuncture training or CTRC nursing personnel will collect approximately two teaspoons (10 mL) of venous blood by peripheral venipuncture and the participant will collect half a cup of urine (20 mL) via a clean-catch method for analysis. Participants will be provided with a handout describing the “low plant diet” (Section I.4.) that they are to follow prior to each study visit, should they qualify for the study. The visit is expected to take 45-60 minutes.

A study clinician will review screening and laboratory results prior to participant enrollment. Participants will be contacted by phone and told whether they qualify for the study or not. Participants meeting all final eligibility criteria will be invited to participate in the intervention phase of the study and will be scheduled for Study Visit 1. Any participants with abnormal health screening or laboratory evaluation will be directed to their primary care physician for treatment and excluded from the study. In the event that a participant does not qualify for the study, their data will be destroyed at the end of the study.

I.4. Study visits 1 and 2

Visit timing: Visit 1 will occur a minimum of 72 hours following the screening visit to ensure adequate time for the low plant diet (Section I.4.), the screening laboratory results and for scheduling of appropriate facilities. Visit 2 will occur approximately 2-4 weeks following Visit 1 to allow for complete wash out of the study intervention (Figure 3).

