I.5. Visit 1 and 2 tolerability phone assessment

Participants will be telephoned the day following each study visit to assess for delayed adverse events and/or complications from the intravenous catheter placement using interviews and a standardized multi-system adverse events questionnaire (Figure 3, Table 2). Participants will be instructed to contact a study clinician if they experience any reactions following the phone assessment, and prior to their second study visit or one-week exit interview.

I.6. Exit interview tolerability assessment

Participants will be telephoned one week following the completion of their second study visit, or first study visit if they elect to drop out of the study, to assess for delayed adverse events and/or complications from the intravenous catheter placement using interviews and a standardized multi-system adverse events questionnaire (Figure 3, Table 2).

Table 2. Schedule of study visits and assessments.

	Screening	Visit 1	Visit 1 + 1 day	Visit 2	Visit 2 + 1 day	Visit 2 + 7 days
Event		Study visit	Phone visit	Study visit	Phone visit	Phone visit
Informed consent	•					
Vitals+	•	•		•		
Health screening, biometric assessment	•	•		•		
Electrocardiogram (EKG)		•		•		
Blood draw (CBC, CMP*) and urinalysis	•					
Low plant diet (starting 48h prior to visit)		•		•		
Single dose of intervention		•		•		
Blood collected at intervals (0-12hr) for bioavailability and antioxidant assessment	•^	•		•		
12-hour urine collection, baseline urinalysis		•		•		
Adverse events (AE) questionnaire		•	•	•	•	•

Study Title: A pharmacokinetic study of *Centella asiatica* in the elderly

Principal Investigator: [name]

IRB#: 17697

Date: Feb 28 2024

Protocol v4.0

Vitals include blood pressure, temperature and pulse rate

* CBC = Complete Blood Count with differential; CMP = Comprehensive Metabolic Panel

[^] Single time point

I.7. Subject participation duration

Including the screening visit, a two to four-week interval between doses, and an exit phone interview for adverse event monitoring, it will take a participant six to eight weeks to complete the study.

J. STUDY DURATION

Recruitment and data collection is expected to begin upon approval from the IRB and FDA and continue for seven months. We estimate a total of four months for final data analysis. Total estimated study duration is eleven months (Table 3).

Table 3. Study timeline.

Activity	Month	1-3	4-6			7-9			10-12		
Finalize product manufacture/quality control											

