Samples will undergo chromatographic separation using an Intersil Phenyl-3 column with an ejection volume of 10 μL . Triplicate analysis will be performed. Gradient elution will be performed using a mobile phase consisting of solvent A (water containing 0.1% v/v formic acid) and solvent B (methanol containing 0.1% v/v formic acid), with a flow rate at 0.4mL/min. HPLC-MS analysis will be performed using a Shimadzu Nexera UHPLC system connected to an AB SCIEX TripleTOF® 5600 mass spectrometer equipped with a Turbo V ionization source operated in the electrospray ionization (ESI) mode will be used. Data-dependent acquisitions (DDAs) will be conducted to obtain precursor and fragment ion information using the negative (ESI-) and positive ionization (ESI+) modes. Level 1 annotations we will be based on accurate mass, fragment ion spectral similarity, and retention time co-elution based on authentic commercially available standards. Putative Level 2 annotations will be based on exact mass, isotopic pattern, and MS/MS spectral data.

K.4. Analysis of total antioxidant compounds

Total antioxidant compounds in plasma will be measured at each time point using the OxiSelect™ kit (Cellbiolabs Inc.) and following the manufacturer's instructions. The assay, performed in 96-well plates, is a quantitative assay for measuring antioxidant potential within plasma samples. Following the reduction of ferric iron (Fe^{3+}) to ferrous iron (Fe^{2+}) by antioxidants in the sample, the kit colorimetric probe develops a blue color that is read at 540-600 nm. The antioxidant potential of samples is determined based on an iron standard curve and results are calculated at Fe^{2+} equivalents (μM) or FRAP value.

K.5. Sharing of results with participants

All screening laboratory results, performed by the CLIA certified OHSU Core Laboratory, will be provided to the participant. If a screening result is found abnormal (an incidental finding), the participant will be instructed to share their result with their primary care provider. Electrocardiograms (EKGs) will be performed at each study visit. If the EKGs are found to be abnormal, the participant will be instructed to share their result with their primary care provider. As there will be no additional laboratory assessments with clinical implications beyond the screening visit, no results from the study will be shared with the research participant or their provider(s).

K.6. Data and specimen banking

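### H.4 names a post-dose laboratory change as a possible withdrawal reason, but no blood chemistry is scheduled after screening, so a silent change in liver enzymes, BUN or creatinine between the two doses has no planned measurement

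*Combined protocol and SAP*

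**What the plan says.** H.4 introduces its list permissively: "A participant may discontinue and/or withdraw and/or be withdrawn from the study for the following reasons". Item 4 of the adverse-event reasons is "Major/clinically significant alteration in laboratory values or biometric assessments after beginning product". No threshold is given. The same section allows withdrawal at the request of the investigator or the primary care physician and for other health reasons. It also ends the study if two participants stop because of intervention-related adverse events.

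I.3 places the safety laboratory work at screening: "A non-fasting plasma and urinary laboratory evaluation (complete blood count, comprehensive metabolic panel and urinalysis) will be performed". In Table 2 the row "Blood draw (CBC, CMP*) and urinalysis" carries one mark, under Screening. A separate row, "12-hour urine collection, baseline urinalysis", is marked at Visits 1 and 2. K.5 explains why no later results will be returned to participants: "As there will be no additional laboratory assessments with clinical implications beyond the screening visit".

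The safety measures planned at the study visits (I.4) are biometrics, vital signs, EKG before dosing and at six hours, and a symptom questionnaire. Follow-up after each visit is by telephone.

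**The concern.** The laboratory part of item 4 has no scheduled blood result to act on once product has been given. That matters because of what the protocol says about the liver and kidney. C.4.4 acknowledges some concern about hepatotoxicity and says there are no human safety data on concentrated water extracts at the two study doses. C.4.2 describes a 30-day rat study of the dried herb in which ALT, AST, BUN and creatinine rose without clinical signs. A symptom questionnaire would miss that pattern. C.4.1 reports one withdrawal for abnormal liver enzymes in an earlier trial of a related triterpene product, with recovery on stopping.

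Two things are at stake. All eight participants would receive dose two with no scheduled chemistry check after dose one. And the preliminary acute safety data described in section P would say nothing about post-dose blood chemistry. The C_max, AUC and t_max endpoints are not involved.

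**Working it through.** The plan gives no figure to reproduce on this point. The check compares the criterion with the schedule, then sizes the exposure and the remedy.

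**Criterion against schedule**

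| Measure that could inform H.4 item 4 | Screening | After dose one, before dose two | After dose two |
|---|---|---|---|
| CBC and CMP (Table 2, I.3, K.5) | 1 | 0 | 0 |
| Urinalysis (Table 2) | yes | Visit 2 baseline | none marked separately |
| Biometrics and vital signs (I.4, Table 2) | yes | yes | no fixed post-dose time given |
| EKG (I.4) | no | yes | yes, 6 h |

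The biometric half of item 4 has data. The laboratory half has at most a urinalysis. The text describes visit urine only as a measure of metabolite excretion (I.4) and as a pooled assay blank (K.3), so its clinical use is unclear. N.1 works from questionnaire items, so a silent chemistry change would not enter attribution. The Figure 3 image is not available, but Table 2 and K.5 agree.

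**Exposure.** C.4.4 takes the product as about 4% triterpenes.
- 2 g × 0.04 = 80 mg; 4 g × 0.04 = 160 mg; sum 240 mg over the whole study.
- With the range in section E (0.94–2.41%), the 6 g total delivers 6,000 × 0.0094 = 56 mg to 6,000 × 0.0241 = 145 mg.
- In the earlier trial the daily dose in weeks 9–52 was 240 mg. The whole study therefore delivers at most about one day of that exposure. This covers triterpenes only; the product is a crude extract with other constituents.

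**Time to act on a Visit 1 result.** I.4 says "Visit 2 will occur approximately 2-4 weeks following Visit 1", and I.2 says "participants will be called three days prior to their second study visit to ask if they wish to continue their participation". The window is 14 − 3 = 11 days to 28 − 3 = 25 days, so no same-day result is needed.

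**Clock time of the draw.** The fast starts at 9 PM and lasts 10–12 h, so dosing is at about 7–9 AM. The 12-hour draw falls at about 7–9 PM and the 10-hour draw at about 5–7 PM.

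**Blood volume**
- Planned per visit: 15 + 12 × 10 = 135 mL.
- Planned per participant: 10 + 2 × 135 = 280 mL.
- Two CMPs in separate tubes, at an assumed 3–5 mL each: 6–10 mL, or 6/280 = 2.1% to 10/280 = 3.6%. None extra if the existing tubes serve.

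**Tests.** 2 × 8 = 16.

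**Chance flags.** Assume 2.5–5% of results fall outside the reference range by chance, and count ALT, AST, BUN and creatinine.
- All results: 4 × 2 × 8 = 64, giving 1.6 to 3.2 expected flags.
- Visit 1 results alone, the only ones that could defer dose two: 4 × 8 = 32, giving 0.8 to 1.6.

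**The case against.** The strongest reply is that the omission is a disclosed and defensible choice. H.4 is a permissive list and promises no scheduled testing. A.3 defines tolerability by interviews, biometrics, vital signs and questionnaires. An IND was obtained, and its content cannot be seen here, so the lack of a stated reason can be asserted only of this document. The single-dose toxicology, which is closest to this design, is reassuring. Rats given 2,000 mg/kg once showed no deaths or treatment-related gross changes over 14 days, and mice given up to 4,000 mg/kg showed no deaths in 24 hours (C.4.2), although these were other extracts. C.4 cites six weeks of a concentrated extract at up to 1 g daily without enzyme change. The adverse liver signals with a stated exposure came from repeated dosing. All of this stands, and it keeps the expected risk low.

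Testing also has costs. Chance flags could feed the two-participant stopping rule or lose participants, and L.2 needs seven for AUC, while losing two of eight leaves six. Holding dose two for a same-day result would lengthen the fast in period 2 only, in a crossover that uses fasting to standardise absorption. The fasting point is decisive against holding dose two for a same-day result. The point about flags is met largely by the criterion itself, which asks for a clinically significant change, and by a deferral rule set in advance.

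A reader might infer that H.4 contradicts Table 2, or that a kidney change could surface only through a for-cause test. The documents do not support either. The list is permissive, its biometric half is measured, the Visit 2 urinalysis might show gross kidney change, and a physician's request is an accepted reason. The protocol describes no procedure for unscheduled tests but does not exclude them.

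**Conclusion.** The point holds as a gap in safety measurement, and it is modest. Zero of eight participants have scheduled blood chemistry after dosing, so the blood-chemistry part of H.4 item 4 has no planned data, and a silent change in liver enzymes, BUN or creatinine between doses would probably pass unseen. Unscheduled testing does not fill the gap, because a silent change gives no cause to test.

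It would be wrong to read this as evidence that participants face a material liver hazard, or that the pharmacokinetic results are compromised. Total triterpene exposure is at most about 240 mg, and nothing in the primary analysis depends on chemistry.

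The conclusion rests on Table 2 and K.5 as written. The assumptions are the tube volume, the out-of-range rate, and clinical laboratory acceptance of the planned samples. The change is worth making because it is cheap, although its coverage is partial.

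**What to change.** 1. Run a CMP, including ALT, AST, BUN and creatinine, on the existing Visit 1 12-hour draw, or on the 10-hour draw if the laboratory cannot take evening samples. A study clinician reviews it against the screening panel by the call three days before Visit 2.
2. Run a CMP on the existing Visit 2 pre-dose draw, for Aim 2 reporting and follow-up. Do not hold dosing for the result, so that the fast stays equal across periods.
3. State in advance which Visit 1 result defers dose two. The documents give no threshold, so the study clinicians must set it.
4. Amend Table 2 and K.5, including how an abnormal result reaches the participant.

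Cost: 16 routine tests, no extra visit or needle stick, and 0–10 mL of extra blood per participant. The zero assumes the clinical laboratory accepts the tubes already drawn; I.4 puts the baseline sample in a heparinized tube. Some chance flags will need clinical judgement.

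Limits: 12 hours may be too early, and two to four weeks too late, for a delayed or short-lived change. Neither sample follows dose two. The Aim 2 report should say so.

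If chemistry is not added, limit H.4 item 4 to the measures actually collected and to for-cause tests, and state in the Aim 2 report that liver and kidney blood chemistry was not assessed after dosing. That costs only wording.

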Eight non-demented elderly volunteers (n=4 each female and male) 65-85 years of age will be screened and enrolled in the study. We estimate that we will need to screen approximately twelve potential participants to meet the eight volunteers needed to complete the study. We expect a 10% drop out rate. We are still powered to see changes from baseline and differences between doses with a 25% drop out rate resulting in 6 subjects.

F.2.2. Inclusion and exclusion criteria

Inclusion criteria:

1. Age 65-85, male and female
2. Sufficient English language skills to complete all tests
3. Sufficient vision and hearing to complete all tests
4. No known allergies to *Centella asiatica*, (**excipients redacted**) or any of their derivatives
5. Willingness to discontinue all botanical dietary supplements for one week prior to and during each study visit
6. Willingness to comply with a 48-hour low plant diet for each study visit
7. Absence of significant depression symptoms (Geriatric Depression Scale-15 score of <12)
8. Body Mass Index (BMI) greater than 17 and less than 35 at screening
9. Non-demented, defined as Clinical Dementia Rating (CDR) score of zero and Mini Mental State Examination (MMSE) score >28
10. General health status that will not interfere with the ability to complete the study

Exclusion criteria:

1. Current smoking, alcohol or substance abuse according to DSM-V criteria
2. Women who are pregnant, planning to become pregnant or breastfeeding
3. Men who are actively trying to conceive a child or planning to within three months of study completion
4. Severe aversion to venipuncture
5. Abnormal laboratory evaluation indicating asymptomatic and untreated urinary tract infection
6. Cancer within the last five years, with the exception of localized prostate cancer (Gleason Grade <3) and non-metastatic skin cancers
7. Comorbid conditions such as diabetes mellitus, kidney failure, liver failure, hepatitis, blood disorders, clinical symptomatic orthostatic hypotension, and unstable or

Study Title: A pharmacokinetic study of *Centella asiatica* in the elderly

Principal Investigator: [name]

IRB#: 17697

Date: Feb 28 2024

Protocol v4.0

- significantly symptomatic cardiovascular disease
- 8. Significant disease of the central nervous system such as brain tumor, seizure disorder, subdural hematoma, cranial arteritis, or clinically significant stroke
- 9. Major depression, schizophrenia, or other major psychiatric disorder defined by DSM-V criteria

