Low phytochemical “plant” diet: Due to the nature of the bioactive compounds from *Centella asiatica*, participants will be required to adhere to a “low plant diet” designed by the Oregon Clinical and Translational Research Institute Bionutrition Department at OHSU. They will comply with this diet for 48 hours prior to each study visit, for which they will be given a handout at the screening visit. The diet is essentially limiting intake of fruits, vegetables, coffee, whole grains, chocolate and tea, which may contain compounds similar to those found in *Centella asiatica*. Participants will be provided with food conforming to this diet for the duration of each study visit including three full meals and snacks as needed. To assess for success of the diet, a small amount of the blood obtained at the screening visit will be analyzed for the presence of the bioactive compounds while the participant is following their normal diet and then compared to baseline levels at each study visit. To monitor for dietary compliance, a 48-hour diet diary will be provided to each participant to be filled out each day and brought to each study visit. The diary will also include areas for documenting supplement and medication usage. This has been submitted with this protocol for approval.

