Biological levels of *Centella asiatica* triterpenes, caffeoylquinic acids, and their metabolites will be assessed in both plasma and urine using high-performance liquid chromatography coupled to tandem mass spectrometry (HPLC-MS/MS). We will also conduct additional targeted and untargeted analysis to fingerprint the *Centella asiatica* derived compounds found in plasma and urine samples.

Plasma calibration curves will be made using pooled baseline human plasma from the study participants (one teaspoon (5 mL)/participant) separated by gender. The blank plasma will be spiked with increasing doses of commercially available reference triterpenes, caffeoylquinic acids and known metabolites, as well as appropriate internal standards (see below). If the blank plasma is found to contain traces of the analytes, we will calculate the true concentration by back extrapolation using the method of standard addition. A pooled baseline urine sample taken from participants (separated by gender) will be used as a "blank" urine sample for spiking with standards.

Triterpenes; Plasma (200 μ l) and urine samples (3000 μ l) will be mixed with phosphoric acid and internal standard (chrysin) before incubation with *E. coli* glucuronidase and *S. aerogene* sulfatase to release the analytes of interest from glucuronide and sulfate conjugates. Incubated samples are passed through a Supelco Supelclean™ C8 column, washed with dilute aqueous acetic acid to remove salts, and eluted with ammoniacal methanol. The eluant is vacuum dried, reconstituted in 200 μ l of 1:1 methanol: ammonium acetate and filtered through a 0.2 μ M spinfilter to remove residual particles before analysis. HPLC-MS/MS will be performed on an Applied Biosystems Q-Trap 4000 LC-MS instrument. The analytical method to be used is a modification of that described by Nair et al.(Nair, Menon et al. 2012) Chromatographic separation will be achieved using a Poroshell 120 EC18 column and methanol:ammonium acetate gradient. Triterpenes will be detected as their ammonium adducts with positive ion mode electrospray ionization using the following MS/MS transitions: AA (506/453) and MA (522/451), and chrysin will be detected as the molecular ion (255/255).

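### The visit and reminder timings do not guarantee the one-week botanical-supplement stop in inclusion criterion 5: as little as three days is possible

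*Combined protocol and SAP*

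**What the plan says.** The combined protocol and SAP deals with botanical supplements in several places.

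- **F.2.2, inclusion criterion 5:** "Willingness to discontinue all botanical dietary supplements for one week prior to and during each study visit".
- **F.2.2.1.3, prohibited interventions:** herbal supplements and other products containing plant extracts are listed, with no time window.
- **I.4, visit timing:** "Visit 1 will occur a minimum of 72 hours following the screening visit". The reasons given are "to ensure adequate time for the low plant diet (Section I.4.), the screening laboratory results and for scheduling of appropriate facilities"; the supplement stop is not among them. Visit 2 follows about 2-4 weeks after Visit 1.
- **I.2, call before Visit 2:** "participants will be called three days prior to their second study visit to ask if they wish to continue their participation in the study". In the same call, "participants will also be reminded of their upcoming study visit, to stop necessary supplements, and begin the necessary dietary changes".
- **I.4, diary:** "a 48-hour diet diary will be provided to each participant"; supplement and medication use is recorded in it.
- **Table 2:** there is a row for the 48-hour diet and none for the supplement stop.

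Two provisions bear on the consequences. K.3 says that "Plasma calibration curves will be made using pooled baseline human plasma from the study participants", pooled by sex, with standard addition to be used if the blank contains traces of the analytes. I.4 compares analyte levels in screening blood with the baseline level at each visit.

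**The concern.** The entry criterion sets seven days, while the operational steps are built around two or three. A participant who takes a botanical product until screening, qualifies, and is booked at the earliest permitted date would reach Visit 1 after three days. One who resumes between visits and stops when the call comes would reach Visit 2 after three days. In neither case would the diary show that the week had been missed.

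What is at stake is the pre-dose level. If a product contained Centella compounds, caffeoylquinic acids or related phenolics, and some remained at dosing, it would add to the measured Cmax and AUC, which are primary endpoints (A.3). Dose effects are judged on within-subject differences (L.1). Equal residue at both visits would largely cancel in a simple difference, but residue at one visit only would enter the dose contrast. With eight participants, one such case carries weight.

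**Working it through.** **Inputs.** Required stop: 7 days (F.2.2). Shortest interval from screening to Visit 1: 72 h (I.4). Call before Visit 2: day -3 (I.2). Diary: 48 h (I.4). Gap between visits: 2-4 weeks (I.4). Exit call: one week after Visit 2 (I.6). Total participation: 6-8 weeks (I.7).

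**1. Guaranteed time before Visit 1.** 72 / 24 = 3 days. Shortfall against criterion 5: 7 - 3 = 4 days (96 h), or 4/7 = 57% of the days.

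**2. Reminder before Visit 2.** The call at day -3 comes 7 - 3 = 4 days after the week should have begun. The 14-28 day gap leaves room for an earlier call.

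**3. Verification.** The diary covers 48 / 24 = 2 days, so 7 - 2 = 5 of the seven days go unrecorded.

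**4. Expected timetable.** Screening to Visit 1 = total weeks - gap between visits - 1 week to the exit call.

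- Matched pairings: 6 - 2 - 1 = 3 weeks; 8 - 4 - 1 = 3 weeks.
- Mixed pairings: 6 - 4 - 1 = 1 week; 8 - 2 - 1 = 5 weeks.

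The usual course therefore allows the full week. The shortfall arises at the permitted minimum.

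**5. What four days could mean for residue.** The documents give no human half-life, which is itself a secondary endpoint, so the half-lives below are assumptions. With first-order elimination, the fraction remaining after t hours is 2^(-t / half-life):

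| Assumed half-life | Left at 72 h | Left at 168 h |
|---|---|---|
| 6 h | 0.02% | <0.001% |
| 12 h | 1.6% | 0.006% |
| 24 h | 12.5% | 0.8% |
| 48 h | 35% | 8.8% |

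The extra four days make no practical difference at 6 h and a clear one at 24 h or longer. These are fractions of an unknown starting level, not concentrations.

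**6. Pooled blank.** With four participants per sex giving 5 mL each (F.2.1, K.3), one participant supplies 1/4 = 25% of a pool.

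**The case against.** The strongest reply is that the protocol already covers the point. The 72 hours is a floor, and clinician review of results, a qualification call and scheduling all precede Visit 1 (I.3). Eligibility is checked by phone before screening (I.1), and herbal products are separately prohibited. The telephone script, consent form and diary are not reproduced in the public document, and any of them may carry a day -7 instruction. Traces in the blank are foreseen, and baseline is compared with screening. The protocol accepts 48 hours for coffee, tea, fruit and vegetables, which it says may contain similar compounds. It also plans to estimate half-life from 12-hour profiles, which suggests elimination over hours.

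Much of this stands. It removes any claim that three days is typical, and it makes material residue uncertain. It does not close the gap in four respects:

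- Criterion 5 tests willingness, not an actual stop, and participants learn whether they qualify only after the screening results are reviewed.
- The prohibition has no window. If it runs throughout the study, it fits neither a one-week criterion nor a day -3 reminder to stop.
- Standard addition deals with calibration, not with a participant's own pre-dose level. The baseline comparison is described as a check on the diet, with no threshold or action, and L.1 describes no correction of an individual's Cmax or AUC.
- The 48-hour diet rule might be a reason to shorten the supplement stop, but the protocol does not offer it as one.

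**Conclusion.** The passages do not agree. The timings guarantee three of the seven days that criterion 5 names, and the diary cannot show whether the other days were kept. This rests on the text and simple date arithmetic. The effect on the endpoints is a possibility of unknown size: it needs a participant whose supplement contains the analytes, a short interval or late stop, and a half-life long enough to leave residue.

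A reader might infer more than the documents support:

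- *That the schedule limits participants to three days.* It does not; it permits as few as three, and the expected timetable has room for seven.
- *That the day -3 call is the first instruction to stop.* The text calls it a reminder, and earlier materials are not available to check.
- *That baseline samples and the pooled blank will contain the analytes.* Nothing in the documents shows this, and standard addition provides for traces in the blank. The 57% counts calendar days, not bias. Setting the lowest mouse Cmax (15 ng/mL) against the 5 ng/mL bottom calibrator says nothing about supplement residue.

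This is a modest inconsistency, worth correcting because it touches the primary endpoints and costs very little to repair.

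**What to change.** Reconcile F.2.2 (criterion 5), F.2.2.1.3, I.2 and I.4 so that they state one supplement rule with one window. Which way is for the sponsor to decide:

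- **Keep the one-week rule.** For supplement users, tie the earliest Visit 1 to a confirmed stop one week before; the 72-hour floor can remain for non-users. Move the supplement reminder for Visit 2 to at least seven days ahead. Add the date of last botanical use to the diary.
- **Revise criterion 5.** Give the reason for the new period, and make the reminder and diary match it.

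Under either choice, state the window for the prohibition in F.2.2.1.3.

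The cost of keeping the one-week rule is one earlier call, one diary line and at most four days' later scheduling for some participants, which the 6-8 week participation can absorb. The recorded date would let the analyst show that the stop was kept, or help to explain a raised pre-dose level.
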